## 12.3.3. Exploratory endpoints

- Completeness and accuracy of routinely collected record linked data compared with data collected directly from participating hospitals.
- Estimation of disease-related outcomes as defined above using routine data for patients entered into the main trial. For patients pre-screened but who do not subsequently enter the trial the starting point for these endpoints would be the date of pre-screening.

## 12.4. Statistical Analysis Plan

Time from registration to ipsilateral breast disease will be analysed using survival analyses methods (e.g. Kaplan Meier graphs) and will include all patients registered to the study (i. by protocol directed treatment recommendation and ii. By treatment received). Patients who have a regional or distant relapse, second cancer or death event prior to an ipsilateral breast disease event will be censored at the date of this event. Ipsilateral breast disease rate estimates at 5 years will be reported with 95%CIs. Rates in patients allocated to avoid radiotherapy and those who are allocated to radiotherapy will not be formally compared. The probability of the true rate of local relapse not being greater than 5% by 5 years will also be presented.

Secondary disease related endpoints will be analysed using the same methodology as for the primary endpoint. Estimates at 5 and 10 years will be reported with 95%Cls. Rates in patients allocated to avoid radiotherapy and those who are allocated to radiotherapy will not be formally compared. Patients who have had a previous contralateral breast cancer are eligible for the study but will not be included in the analysis of contralateral breast second primary cancer rates. In addition to the ITT analysis of the other secondary endpoints, a sensitivity analysis will exclude patients who have had a previous contralateral breast cancer.

Routinely collected record-linked, baseline, treatment and disease-outcome data will be compared with local centre data completion via eCRFs. Concordance between data sources will be presented by reporting the proportion of patients with matching data between the CRF and relevant routine data items. The definition of what is classed as matching will vary for each data item (e.g. some dates could have acceptable time-windows) and will be specified in the Statistical Analysis Plan. In addition, routinely collected baseline and treatment data will be tabulated for patients who enter pre-screening but not the main trial. Disease related outcomes will also be analysed using survival analysis methods and the proportion event-free at 5 and 10 years will be reported by type of follow-up (CRF or routine data). The absolute differences and corresponding 95%CIs between methods will then be calculated for patients entering the main trial.

Further details of analysis methods will be specified in a Statistical Analysis Plan in accordance with ICR-CTSU Standard Operating Procedures.

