#### 2. STUDY OBJECTIVES

#### 2.1. Primary Objective

 To assess the risk of any ipsilateral invasive and DCIS breast disease by 5 years following omission of postoperative breast radiotherapy (given according to local practice)

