Patients at a 'very low' risk of recurrence still have the option to have radiotherapy and likewise those at slightly higher risk still have the option not to have radiotherapy. PRIMETIME will record all registered patients irrespective of their treatment choice, but their final treatment decisions must be recorded and follow up must be according to the treatment the patient receives.

All patients registered into the study, regardless of their risk category or whether or not they receive radiotherapy will be prescribed at least 5 years adjuvant endocrine therapy and any additional anti-cancer treatment in accordance with local practice. Patients will attend follow up clinic visits in accordance with local practice.

Patients receiving radiotherapy will have annual mammography according to local practice. Patients not receiving radiotherapy will require annual mammography for 10 years therefore mammograms performed according to local practice should be supplemented with additional scans to ensure annual mammography for 10 years. For all patients registered in PRIMETIME, centres should inform ICR-CTSU of disease relapse, new primary disease or death until the end of study. Centres will be prompted to provide a patient status update on an annual basis.

Study data will be corroborated by linkage with routine data available for example via the National Cancer Registration Service and Hospital Episode Statistics.

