#### 8.5.2. Patients who receive radiotherapy

- Patients should have annual mammograms according to local practice.
- Patients should attend clinic visits according to local practice.
- ICR-CTSU will contact research sites annually to request an update on patient status. Reasonable efforts should be made to contact patients annually for ten years.
- Information collected at follow up visits and the annual mammogram should be recorded in the PRIMETIME eCRF.

As described above, it is intended that research sites will follow up all patients annually for ten years. Over the course of the study, the study team aim to transfer the provision of long term follow up data from research sites to routine data sources where the patient has provided consent to do so and where the required data point is available. This is intended to relieve the burden of long term follow up on research sites, and as a move towards this, data collection in the eCRF for patients where no disease event has occurred is minimal.

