#### 12. STATISTICAL CONSIDERATIONS

#### 12.1. Statistical Design and Sample Size Justification

The primary objective is to assess the safety of avoiding radiotherapy in terms of risk of ipsilateral breast disease. In the cohort of patients for whom selective avoidance of radiotherapy is advocated, the ipsilateral breast disease rate is expected to be ≤4% at 5 years. The sample size has been calculated based on excluding at most a 5% ipsilateral breast disease rate at 5 years within this group using a one-sided 97.5% confidence interval. Allowing for 5% of patients to be non-evaluable at the time of primary endpoint analysis (due to patients progressing with metastatic BC or dying from unrelated causes) gives a total of 1550 patients required in the no radiotherapy cohort.

It is expected approximately 70% of patients screened for PRIMETIME will be defined as very low risk using the IHC4+C score, and assuming a 7.5% non-compliance with the screening stage, 2400 patients will need to be screened to ensure sufficient numbers enter the no radiotherapy cohort. Therefore, it is estimated that approximately 660 patients who are screened for PRIMETIME will be advised to receive radiotherapy according to standard practice. These patients will provide an estimate (and 95%CI) of ipsilateral breast disease rates following radiotherapy in a largely low risk patient group (as opposed to a very low risk group) however they will not form a direct comparator group due to the inherent differences in their risk profile. For example, with 660 patients and 16 ipsilateral breast disease events, a 2.4% ipsilateral breast disease rate with 95% CI 1.4-3.9% can be estimated.

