## A3. Why is this the preferred design of PRIMETIME?

A cohort based study design is proposed in preference to a randomised controlled trial (RCT) testing breast radiotherapy (RT) versus no RT. Such a design is considered preferable for several reasons:

- (i) The effect of RT in reducing ipsilateral breast disease risk after breast conservation surgery for early breast cancer (rate ratio at 10 years 0.40, SE 0.09) has been fully quantified by RCTs involving 8000 women and >10 years of follow up (1). The proposed design focuses exclusively on testing the *need* for RT in a patient population considered to have such a low risk of local recurrence that the potential absolute gain from RT is considered so small as to not outweigh the established risks associated with breast RT.
- (ii) A review of the worldwide evidence would suppose that within an appropriately defined low risk patient population a cohort of patients treated with surgery and endocrine therapy (as standard) but without RT, would result in local control rates which may be a little higher than what would have been observed if all patients had received RT but given the salvageable nature of such relapses would be expected not to have an adverse impact on long term disease-free and overall survival. Designing a randomised trial to assess such outcomes would result in a trial requiring a large number of patients, with expected challenges associated with randomisation and follow up over many years
- (iii) Conducting a study whereby one defines the limits of acceptability for the upper threshold for 5 year ipsilateral breast disease rate without RT, is deemed preferable and of greater clinical utility by health care practitioners and patient advocates. This concept has been employed previously in breast cancer trials [26]. The concept has also been discussed and developed with UK clinicians and patient advocates, with a recent survey of UK Breast Intergroup members (September 2014) survey showing more than 90% (50/55) support for a case-cohort design. In addition, the case-cohort design has unanimous support from the NCRI Breast Clinical Studies Group (discussed June & November 2014).

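### Section 12.4 does not say which analysis set carries the 5% limit, and neither stated set isolates very-low-risk women who omitted radiotherapy

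*Protocol*

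**What the plan says.** The protocol describes the population for its main question in several ways.

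- Section 2.1 states the primary objective by treatment actually omitted: "To assess the risk of any ipsilateral invasive and DCIS breast disease by 5 years following omission of postoperative breast radiotherapy". Appendix A3, item (iii), likewise places the limit on the 5-year rate without radiotherapy.
- Section 12.1 starts from the recommendation: "In the cohort of patients for whom selective avoidance of radiotherapy is advocated". For these women it anticipates a 5-year rate of at most 4%, and the design target is "excluding at most a 5% ipsilateral breast disease rate at 5 years within this group using a one-sided 97.5% confidence interval". The same paragraph then calls the resulting 1550 women the no-radiotherapy cohort.
- Section 12.4 says the primary analysis "will include all patients registered to the study (i. by protocol directed treatment recommendation and ii. By treatment received". It then promises the probability that the true rate does not exceed 5% by 5 years, without naming the set.
- Section 12.5 has the IDMC monitor the no-radiotherapy cohort, again without defining it.

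Deviation is allowed both ways. Under section 3, very-low-risk women "still have the option to have radiotherapy and likewise those at slightly higher risk still have the option not to have radiotherapy"; section 8.2 repeats this. The study schema footnote has the IDMC monitor the deviation rate, but no expected rate is given.

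**The concern.** The descriptions in sections 2.1, 12.1, 12.4 and A3 coincide only if every woman follows the recommendation. Once some deviate, there are three groups:

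1. **By recommendation:** every woman classed very low risk, including those who chose radiotherapy.
2. **By treatment received:** every woman without radiotherapy, including low-, intermediate- and high-risk women who declined it.
3. **The overlap:** women classed very low risk who omitted radiotherapy. Section 12.4 does not list this set.

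In a randomised superiority comparison, dilution by non-compliance is usually conservative. Here there is no randomised comparison to protect. Women in the first set who had radiotherapy carry a lower event rate, which pulls the estimate towards a finding that omission is safe. The second set is pulled the other way by women the biomarker did not select. The two can fall on opposite sides of 5%, and the protocol does not say which decides.

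**Working it through.** **Inputs from the protocol.** Section 12.1: expected rate 4%, limit 5%, one-sided 97.5% confidence interval, 5% non-evaluable, 1550 women, 70% very low risk, 7.5% non-compliance at the screening stage, 2400 registered. Appendix A3: radiotherapy effect "rate ratio at 10 years 0.40, SE 0.09". Section 1.1 says radiotherapy halves recurrence, so a ratio of 0.50 is used as the alternative.

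**Assumptions not in the protocol.** A share d of very-low-risk women taking radiotherapy, from 2% to 20%; the rate ratio r also holding at 5 years; equal baseline risk in women who deviate; and, for the second set, a 6% to 10% rate without radiotherapy in higher-risk women.

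**Reproducing 1550.** n = 1.96² × 0.04 × 0.96 / 0.01² = 1475.1, so 1476. Then 1476 × 1.05 = 1550, or 1476 / 0.95 = 1554. The sample size is a precision calculation.

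**Reproducing 2400.** 2400 × 0.925 × 0.70 = 1554 without radiotherapy, and 2400 × 0.925 × 0.30 = 666 with it (section 12.1 says about 660). The 7.5% is lost at screening. Every very-low-risk woman is counted as omitting radiotherapy.

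**Success rule.** Evaluable: 1550 × 0.95 ≈ 1472. The exact upper 97.5% bound is 4.988% with 57 events and 5.064% with 58, so 5% is excluded at 57 events or fewer.

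**By-recommendation set.** Rate in the set = p × [1 − d(1 − r)], with p the true risk without radiotherapy. With p = 5%, the chance of wrongly excluding 5% is P(X ≤ 57 | n = 1472, rate in the set).

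| d | rate, r = 0.40 | wrong exclusion | rate, r = 0.50 | wrong exclusion |
|---|---|---|---|---|
| 0% | 5.00% | 2.4% | 5.00% | 2.4% |
| 2% | 4.94% | 3.0% | 4.95% | 2.9% |
| 5% | 4.85% | 4.2% | 4.88% | 3.9% |
| 10% | 4.70% | 7.2% | 4.75% | 6.1% |
| 20% | 4.40% | 17.8% | 4.50% | 13.5% |

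Put the other way, a rate of 5% in this set corresponds to a true risk without radiotherapy of 5% / [1 − d(1 − r)]: about 5.3% at d = 10%, and 5.6% to 5.7% at d = 20%.

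**By-treatment-received set.** Suppose all 1554 very-low-risk women omit radiotherapy at 4%, and a share e of the 666 others also omit it at rate q. The mixed rate is (1554 × 0.04 + 666e × q) / (1554 + 666e). For q from 6% to 10% this is 4.04% to 4.13% at e = 5%, 4.08% to 4.25% at e = 10%, and 4.16% to 4.47% at e = 20%. The shift is upward and modest.

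**Precision in the overlap.** At d = 10%, 1554 × 0.90 = 1399 women and 1399 × 0.95 = 1329 evaluable. The half-width at 4% is 1.96 × √(0.04 × 0.96 / 1329) = 1.05 percentage points, against 1.00 as designed. At d = 20%, 1243 women and 1181 evaluable give 1.12 points.

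**The case against.** The strongest reply is that section 12.1 ties the 5% limit to the women for whom avoidance is advocated, and the by-recommendation set matches that group exactly. Section 12.4 lists that set first, speaks of women allocated to avoid radiotherapy, and refers to the ITT analysis of secondary endpoints. A reader might infer that both stated sets miss the trial's target; the documents do not support that. The overlap is the target only if sections 2.1 and A3 are read together with the rationale. What stands is that sections 2.1, 12.1, 12.4 and A3 do not agree, and that 12.4 leaves the deciding set open.

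The size rests on a deviation rate the protocol does not give. With none, the three sets coincide; at 2% the error barely moves. The 7.5% in section 12.1 concerns screening and cannot be borrowed. This limits the claim about size but does not affect the direction of the bias.

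The two sets err in opposite directions, so reporting both gives a rough bracket. That helps interpretation but does not say what is concluded if they disagree.

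A reader might also infer a surveillance bias from section 8.5.2, "Patients should have annual mammograms according to local practice". Section 8.5.1 also refers to local practice for the first 5 years in women without radiotherapy, so no clear contrast is shown within the primary window.

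Finally, a reader might infer that the overlap should be the only test set. It is defined by a choice made after registration; if women at higher underlying risk are the ones who opt for radiotherapy, it too would look falsely safe. It belongs beside the by-recommendation set and should not replace it.

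The SAP is not at hand and may settle the point. Even so, the protocol itself fixes the two groupings and gives inconsistent population labels.

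**Conclusion.** The concern holds in a limited form. The protocol's population wording is inconsistent, section 12.4 does not name the set that carries the 5% statement, and neither stated set isolates very-low-risk women who omitted radiotherapy.

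If the by-recommendation set decides alone, the error runs in the unsafe direction. The one-sided error goes from 2.4% to about 3% at 2% deviation, 4% at 5%, 6 to 7% at 10% and 13 to 18% at 20%. These figures assume a true risk without radiotherapy of exactly 5%, 1472 evaluable women, a rate ratio of 0.50 to 0.40 applying at 5 years, and equal baseline risk in women who deviate. The effect is negligible if deviation is rare and material from about 10%. Because the main safety conclusion depends on the choice of set, it should be settled before results are seen.

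**What to change.** 1. **Section 12.4:** add the set of registered women classed very low risk by IHC4+C who did not receive breast radiotherapy as part of initial treatment. State that omission is concluded to be safe only if 5% is excluded both in this set and in the by-recommendation set. Keep the set of all women without radiotherapy as supportive. Because both conditions must hold, no multiplicity adjustment is needed.
2. **Sections 12.1, 12.4 and 12.5:** use one definition of the no-radiotherapy cohort.
3. **Section 12.1:** state that 2400 × 0.925 × 0.70 = 1554 assumes no very-low-risk woman takes radiotherapy, and give the precision expected in the added set under a stated deviation rate.

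Giving the precision avoids raising the target. Counting 1550 in the added set at 10% deviation would need 1550 / (0.925 × 0.70 × 0.90) ≈ 2660 registrations instead of 2400.

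The cost is wording and one further analysis; treatment received is already recorded. The downside is that the added set is defined by patient choice and is slightly smaller, so the criterion is a little harder to meet.

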#### 7.1.2. Exclusion Criteria

- 1. Patients with known or suspected lymphovascular space invasion and/or axillary nodal micrometastases or macrometastases.
- 2. Synchronous bilateral breast cancer
- 3. Patients with a past history of malignancy except
  - (i) basal cell skin cancer and CIN cervix uteri or
  - (ii) treated, localised squamous cell carcinoma of the skin or
  - (iii) malignancies treated with curative intent (including contralateral breast cancer and DCIS) and the patient has been disease free ≥5 years;
- 4. Patients who have had an ipsilateral mastectomy;
- 5. Patients who have received neoadjuvant therapy (endocrine or cytotoxic chemotherapy with therapeutic intent) or who are deemed by the MDT to require adjuvant cytotoxic chemotherapy. Note 1: In most instances treatment within a window of opportunity study is not considered of therapeutic intent and will therefore be allowed: please check with the PRIMETIME trial manager if a patient has participated in a window of opportunity study. Note 2: It is recognised that breast surgery may occasionally be delayed for non-clinical reasons. These situations should be discussed with the PRIMETIME Trial Manager prior to patient registration. Consideration will be given to endocrine therapy not exceeding 28 days and the final pathological tumour size not exceeding 15mm (as tumour shrinkage during pre-operative endocrine therapy is possible).
- 6. Patients with mammographically occult breast cancers, ie. present with lump, but not visible on mammogram.
- 7. Patients who are currently receiving endocrine therapy for previous breast cancer.

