#### 12.3.2. Secondary endpoints

- Regional relapse rate (regional relapse is defined as invasive relapse within the axilla, supraclavicular fossa and internal mammary chain)
- Distant relapse rate
- Ipsilateral invasive breast disease rate (defined as invasive disease in the ipsilateral breast)
- Contralateral invasive breast second primary cancer rate
- Any contralateral breast disease rate (defined as invasive and/or non-invasive disease (DCIS) in the contralateral breast).
- Ipsilateral invasive breast local relapse rate (subject to availability of tumour profiling data)
- Ipsilateral invasive breast second primary cancer rate (subject to availability of tumour profiling data)
- Invasive disease free survival defined as time from registration to first event where event can be any invasive local recurrence, regional recurrence, distant recurrence, second primary cancer or death from any cause.

- Breast cancer specific survival defined as time from registration to first event where event can be local recurrence, regional recurrence, distant recurrence, breast second primary or breast cancer death. Death from unknown cause would be classed conservatively as breast cancer death.
- Overall survival defined as time from registration to death from any cause

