### 12.5. Interim Analyses and Stopping Rules

Whilst the primary endpoint includes non-invasive ipsilateral disease, the IDMC will be guided by stopping rules that include invasive disease only. The IDMC will review the emerging ipsilateral

invasive breast disease rates in all cohorts and monitor ipsilateral invasive breast disease rates in the no radiotherapy cohort in particular to ensure that observed interim rates within this cohort are consistent with an overall ipsilateral invasive breast disease rate of ≤1% per year. At each relevant interim analysis, the conditional power of the "final" ipsilateral invasive breast disease rate being ≤1% given the "current" interim analysis ipsilateral invasive breast disease rate will be calculated to help inform the IDMC. This interim monitoring will permit early stopping of the study if evidence emerges that observed incidence of ipsilateral invasive breast disease is higher than expected. The timing of interim analyses will take into account the number of patient-years of follow-up accrued. Whilst it is expected that absolute rates will be the determining measure of ipsilateral invasive breast disease, consideration will also be given to the comparison of the rates of contralateral new breast cancer versus ipsilateral invasive breast disease.

The first interim analysis is anticipated after two years of recruitment and then annually until the primary endpoint analysis. In addition to monitoring ipsilateral invasive breast disease rates, the IDMC will monitor the proportion of patients calculated as "very low" risk according to IHC4+C and rates of non-compliance.

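### Women with a previous contralateral breast cancer are left out of the contralateral second-primary analysis but kept in the main analysis of any contralateral disease, so the headline rates of two nested endpoints rest on different populations

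*Protocol*

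**What the plan says.** All references are to the protocol.

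- **Eligibility (7.1.2).** A past malignancy is a bar, with exceptions. One exception covers "malignancies treated with curative intent (including contralateral breast cancer and DCIS"), provided the woman has been disease free for at least 5 years. A separate criterion bars ipsilateral mastectomy; nothing bars an earlier contralateral mastectomy. Section 12.4 confirms the first point: "Patients who have had a previous contralateral breast cancer are eligible for the study".
- **Endpoints (12.3.2).** Two contralateral endpoints are listed separately. The narrower is "Contralateral invasive breast second primary cancer rate". The wider is "Any contralateral breast disease rate (defined as invasive and/or non-invasive disease (DCIS) in the contralateral breast"). Every event of the first kind is also an event of the second.
- **Analysis populations (12.4).** The default is that "Secondary disease related endpoints will be analysed using the same methodology as for the primary endpoint", which means all registered patients. Women with a previous contralateral breast cancer "will not be included in the analysis of contralateral breast second primary cancer rates". For the rest: "In addition to the ITT analysis of the other secondary endpoints, a sensitivity analysis will exclude patients who have had a previous contralateral breast cancer".

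**The concern.** Section 12.4 makes a deliberate decision about who belongs in a contralateral analysis and applies it to only one of the two contralateral endpoints. By its wording, any contralateral disease is one of the other secondary endpoints, so its main analysis keeps the women whom the narrower endpoint leaves out. No reason for the difference is given.

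Two things follow. First, a woman who had a contralateral mastectomy for her earlier cancer can be registered and would count in the denominator of the wider endpoint although she has no contralateral breast at risk. Second, an invasive contralateral event in a woman with such a history counts in the wider endpoint but cannot count in the narrower one. A reader who sees the two rates in one table will naturally take the difference as the contribution of DCIS, and that would be wrong.

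This is a rule that the protocol states, not a detail left to the statistical analysis plan. A plan written to follow it would inherit the mismatch.

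**Working it through.** The protocol states no figure on this point, so there is nothing to reproduce. The check has two parts.

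**1. The text side by side**

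| | Invasive second primary | Any contralateral disease |
|---|---|---|
| Events (12.3.2) | invasive | invasive and/or DCIS |
| Main analysis (12.4) | without women with a previous contralateral cancer | all registered patients |
| Sensitivity analysis (12.4) | not needed | without those women |

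The narrower endpoint is contained in the wider one by events, but the main analyses do not share a population.

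**2. Possible size (illustration)**

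Inputs, all assumed because the protocol gives none of them:

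- q = share of women with a previous contralateral cancer: 1%, 5% or 10%
- rate in women without that history: invasive 2.0%, DCIS only 0.5%, so any disease r = 2.5%
- k = risk of any contralateral disease in women with the history relative to the others: 0 (no breast at risk) to 2

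Formula, in simple proportions and ignoring censoring:

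reported wider rate = (1 − q) × r + q × k × r

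The relative shift is therefore q × (k − 1). The apparent DCIS component is the reported wider rate minus 2.0%.

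| q | Wider rate, k = 0 | Wider rate, k = 2 | Apparent DCIS component (true 0.5%) |
|---|---|---|---|
| 1% | 0.99 × 2.5% = 2.475% | 1.01 × 2.5% = 2.525% | 0.475% to 0.525% |
| 5% | 0.95 × 2.5% = 2.375% | 1.05 × 2.5% = 2.625% | 0.375% to 0.625% |
| 10% | 0.90 × 2.5% = 2.25% | 1.10 × 2.5% = 2.75% | 0.25% to 0.75% |

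At k = 1 there is no shift for any q. A harsher assumption of k = 4 at q = 5% gives a relative shift of 0.05 × 3 = 15%, that is 1.15 × 2.5% = 2.875%.

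With the same exclusion in both main analyses, the rates in this example are 2.0% and 2.5%, and their difference is the 0.5% DCIS component.

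For scale, the 95% half-width for a rate of 2.5% in 1550 women is 1.96 × √(0.025 × 0.975 / 1550) = 0.78 percentage points (simple binomial). Every shift in the table, at most 0.25 points, is well inside that. The apparent DCIS component moves by the same number of points, but from a much smaller base: at q = 10% it could be halved or raised by half.

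**The case against.** **The matching estimate is already planned.** The sensitivity analysis in 12.4 covers the other secondary endpoints, so any contralateral disease will also be reported without these women. This stands. A reader might infer that the two contralateral rates cannot be compared at all; the document does not support that. What remains is that the comparable figure is labelled a sensitivity result and the headline figure is the one that does not match.

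**The exclusion may have a reason that belongs to one endpoint only.** Calling a tumour a second primary requires telling it from a relapse of the old contralateral cancer, which is hard in women with that history. The wider endpoint makes no claim that the disease is new. This is fair, and section 12.4 gives no reason either way. It weakens the argument about misclassified relapses. It does not touch the women with no breast at risk, nor the difference in populations.

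**The plural in the exclusion clause might cover both contralateral endpoints.** This is weak. Section 12.3.2 names them as separate endpoints, and the plural fits the estimates at 5 and 10 years.

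**Stronger readings to avoid.** A reader might say that the wider analysis contains women who are already affected. Section 7.1.2 requires curative treatment and at least 5 disease-free years, and it excludes synchronous bilateral cancer, so these women have a history and not current disease. A reader might also infer that the data monitoring committee's benchmark is distorted, because section 12.5 says that "consideration will also be given to the comparison of the rates of contralateral new breast cancer versus ipsilateral invasive breast disease" and repeats no exclusion. That is not shown. New contralateral cancer plausibly means the second-primary endpoint, which 12.4 already restricts, and 12.5 expects absolute rates to be the determining measure.

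**Conclusion.** The inconsistency is real on the plain text: the main analyses of two nested contralateral endpoints use different populations, without a stated reason. The wider one may include women not at risk, and the difference between the headline rates is not the DCIS component.

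It is minor. Under the assumed inputs, the shift in the wider rate is 0.025 percentage points at a 1% share and 0.25 points at a 10% share, in either direction, and zero if the risks are equal. The true share and the relative risk are not in the protocol, so neither size nor sign can be settled from it. The primary endpoint, the sample size and the 5% threshold are unaffected, and no formal comparison depends on this endpoint.

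A related ambiguity belongs with it. Section 7.1.2 names DCIS beside contralateral breast cancer, whereas the exclusion in 12.4 speaks only of a previous contralateral breast cancer. Whether women with previous contralateral DCIS are left out is therefore unclear for both endpoints.

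**What to change.** In section 12.4:

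- State that women with a previous contralateral breast cancer are excluded from the main analysis of both contralateral endpoints: invasive second primary, and any contralateral disease.
- State that previous contralateral DCIS is handled in the same way.
- Keep the planned sensitivity analysis for the remaining secondary endpoints.

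If the different treatment of the two endpoints is intended, give the reason in the same place.

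The cost is about one clause. Section 8.3 already has medical history recorded at baseline, and the existing exclusion already relies on it, so no new data collection is expected. The sample size does not change.
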